3.8. Analysis Visit

3.8.1. Definition of Study Day

Study day is the day relative to the date of the first dose of study drug. Study Day 1 will be defined as the day of first dose of study drug administration.

Study day will be derived as follows:

- For post-dose study days: Assessment Date – First Dosing Date + 1
- For days prior to the first dose: Assessment Date – First Dosing Date

3.8.2. Definition of Baseline

In general, the baseline value will be the last nonmissing value on or prior to the first dose date of study drug. If multiple measurements occur on the same day, the last nonmissing value prior to the time of first dose of study drug will be considered as the baseline value. If these multiple measurements occur at the same time or the time is not available, the average of these measurements (for continuous data) or the worst among these measurements (for categorical data) will be considered the baseline value.

Baseline for the primary efficacy analysis is defined as the day of the first dose of study medication (Day 1).

Baseline values for other safety and efficacy endpoints are dependent on the schedule of each assessment.

3.8.3. Analysis Visit

Subject visits or measurements might not occur on protocol-specified days or time points. For parameters that will be summarized by visit, the nominal visit as recorded on the eCRF will be used.

For subjects who prematurely discontinue from the study, the results assessed at early termination (ET) will be assigned to the next scheduled visit where the respective data were scheduled to be collected for summary.

Unscheduled visits will not be included in the by-visit summary tables, but will be included in the listings. An unscheduled visit prior to the first dose of study drug may be included in the calculation of baseline value, if applicable.

3.8.4. Selection of Data in the Event of Multiple Records in a Analysis Visit

Depending on the statistical analysis method, single values may be required for each analysis visit. For example, change from baseline by visit usually requires a single value, whereas a time-to-event analysis would not require 1 value per analysis visit.

If multiple nonmissing numeric observations exist in an analysis visit, records will be chosen based on the following rules if a single value is needed:

- For baseline, the last available record on or prior to the date of the first dose of study drug will be selected. If multiple measurements occur on the same day, the last nonmissing value prior to the time of first dosing of study drug will be considered as the baseline value. If there are multiple records with the same time or no time recorded on the same day, the average (arithmetic or geometric mean, as appropriate) will be used for the baseline value. For the efficacy endpoints, if no measurements occur prior to the time of first dosing of study drug, the first nonmissing value on the first dosing date of study drug will be considered as the baseline value.
- For post-baseline visits:
 - The record closest to the nominal day for that visit will be selected.
 - If there are 2 records that are equidistant from the nominal day, the later record will be selected.
 - If there is more than 1 record on the selected day, the average will be taken, unless otherwise specified.

If multiple valid nonmissing categorical observations exist in a window, records will be selected as follows:

- For baseline, the last available record on or prior to the date of the first dose of study drug will be selected. If there are multiple records with the same time or no time recorded on the same day, the value with the lowest severity will be selected unless otherwise specified.
- For post-baseline visits, the record closest to the nominal day for that visit will be selected. If there are 2 records that are equidistant from the nominal day, the later record will be selected. If there are multiple records with the same time or no time recorded on the same day, the most conservative value (ie, the worst severity) within the window will be selected.

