6.11. Study Assessments

6.11.1. Nasal Samples, Virology, and Antibody Titer

Subjects with unknown RSV status may be tested for RSV at Screening using local laboratory methods. Further nasal sampling will be performed at all study visits PPD [REDACTED]).

Samples must be collected prior to dosing at all dosing visits. Two nasal samples will be obtained, 1 from each nostril, each time nasal sampling is performed. Samples will be stored and shipped to a central laboratory for testing.

In Japan only, 2 nasal swab samples will be collected at Screening; 1 will be processed for RSV locally, while the other will be sent to a central laboratory for analysis. To offset the collection of the additional nasal sample collected at Screening, only 1 sample will be collected for central laboratory analysis at the Baseline visit in Japan. All other visits in Japan will follow the same sampling schedule as the other global sites; 2 nasal swab samples collected, 1 from each nostril for shipment to and analysis by a central laboratory.

At any time during the study, if a bronchoscopy is planned for the same day as nasal sampling, nasal samples should be obtained, if possible, prior to application of any topical anesthetic (eg, lidocaine) in the nostrils. If it is not possible to collect nasal samples from both nares (eg, subject has an NG tube in place), 2 samples should be taken from the same naris and the tube for the second sample should be marked as "back-up." At Visit 9 (Day 22), PPD [REDACTED]

Nasal samples will be analyzed using RT-qPCR to determine RSV viral load, RSV sequencing to evaluate development of resistance (see Section 6.11.2), and a multiplex assay to identify co-infections. PPD

All nasal samples for central laboratory analysis will be collected, placed in individual tubes, and stored/shipped to the central laboratory as per instructions outlined in the Laboratory Manual.

Blood samples will be collected for RSV viremia evaluation (RT-qPCR) at Visits 2, 4, 6, 7, 8, 9, and 10 (Days 1, 5, 9, 13, 17, 22 and 28) prior to dosing, and RSV antibody titers at Visits 2 and 10 (Days 1 and 28). Samples will be processed, stored and shipped to the central laboratory as per instructions outlined in the Laboratory Manual.

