8.2. Analysis Conventions

8.2.1. Analysis Sets

8.2.1.1. Efficacy

The full analysis set (FAS) will include subjects who have an RSV log₁₀ viral load greater than or equal to the LLOQ of the RT-qPCR assay in the pre-dose Day 1 nasal sample, as determined by RT-qPCR at the central lab, and have received at least 1 full dose of IMP. The FAS will be the primary analysis set for all efficacy analyses.

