3.1.2. Full Analysis Set

The Full Analysis Set (FAS) includes all randomized subjects who took at least 1 full dose of study drug, and had an RSV viral load greater than or equal to the lower limit of quantification (LLOQ) of the RT-qPCR assay in the Day 1 nasal sample, as determined by RT-qPCR at the central lab. This is the primary analysis set for efficacy analyses.

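### SAP 3.8.4 lets a nasal sample taken after the first dose serve as the efficacy baseline, and SAP 3.1.2 leaves unclear whether such a subject is in the FAS (minor)

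*SAP*

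**What the plan says.** **Protocol.** Section 6.11.1 states: "Samples must be collected prior to dosing at all dosing visits". Section 6.1.2.1 places the Day 1 baseline assessments, including the nasal swabs, before study drug and bars Screening samples from serving as baseline. Section 8.2.1.1 admits a subject to the FAS on a viral load at or above the LLOQ "in the pre-dose Day 1 nasal sample, as determined by RT-qPCR at the central lab", with at least one full dose taken.

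**SAP.** Section 3.1.2 words the FAS test as a viral load at or above the LLOQ "in the Day 1 nasal sample, as determined by RT-qPCR at the central lab"; the pre-dose condition is absent. Section 3.8.2 sets baseline by date: in general "the baseline value will be the last nonmissing value on or prior to the first dose date of study drug". It defines the primary efficacy baseline simply as Day 1. Section 3.8.4 opens its baseline rule with the same date-based wording and then adds a fallback. For efficacy endpoints, it says, "if no measurements occur prior to the time of first dosing of study drug, the first nonmissing value on the first dosing date" is taken as the baseline value.

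The baseline value enters every change score in the DAVG (SAP 6.1.1) and is a covariate in the ANCOVA (SAP 6.2.1). The FAS is the analysis set for both co-primary endpoints and the secondary endpoint (SAP 6.2 and 6.3.2).

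**The concern.** A baseline should be a value that treatment cannot have touched. If a site doses first and swabs later the same day, the SAP makes the later swab the baseline. Any drug effect already present lowers that baseline, so the subsequent fall looks smaller and the covariate is no longer a pre-treatment variable.

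The looser FAS wording raises a related question. Under the protocol, a subject with no pre-dose Day 1 sample is outside the FAS whatever a later swab shows, so membership never depends on response. Under a literal reading of the SAP, the same subject enters if the post-dose swab is quantifiable and stays out if it is not. Membership in the analysis set for LRTC and for ventilation or death could then turn on a value affected by treatment.

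**Working it through.** **1. The provisions side by side**

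| Question | Protocol | SAP |
|---|---|---|
| When is the Day 1 swab taken? | Before dosing (6.1.2.1, 6.11.1) | Before dosing on dosing days (Appendix 1, footnote f) |
| What is the efficacy baseline if there is no pre-dose value? | No substitute; Screening samples barred | First non-missing Day 1 value (3.8.4) |
| Which sample decides FAS entry? | Pre-dose Day 1 (8.2.1.1) | Day 1 (3.1.2) |

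For a subject swabbed only after dosing:
- With a quantifiable swab, the subject is out under the protocol, in under a literal SAP reading, and out if the SAP wording is shorthand for pre-dose.
- With a swab below the LLOQ, the subject is out under all three.

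So the two FAS definitions can differ only over late-swabbed subjects with a quantifiable result.

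**2. The plan's own power figures** (Protocol 8.8, SAP 1.3)

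- DAVG: difference 1 log10, SD 2, 100 per arm, two-sided 0.01. SE = 2 × √(2/100) = 0.283. Power = Φ(1/0.283 − 2.576) = Φ(0.96) = 0.831, which agrees with the stated figure of over 80%.
- LRTC: 30% versus 10% (reading the 20% reduction as percentage points), two-sided 0.04. Power is 0.937, which agrees with the stated figure of over 90%.
- Either endpoint, if independent: 1 − (1 − 0.831)(1 − 0.937) = 0.989, which agrees with the stated figure of over 95%.

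**3. Size of the DAVG bias**

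Let f be the share of presatovir subjects with a post-dose baseline and d the drug-specific log10 fall before that swab. The documents give neither; the range f = 2-5% and d = 0.1-0.5 is assumed. Each affected baseline is d too low, so every later change is d too small. The DAVG difference therefore shrinks by at most f × d.

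| f | d | f × d | Difference left | DAVG power |
|---|---|---|---|---|
| 2% | 0.1 | 0.002 | 0.998 | 0.830 |
| 5% | 0.25 | 0.0125 | 0.9875 | 0.820 |
| 5% | 0.5 | 0.025 | 0.975 | 0.808 |
| 10% (beyond the range) | 0.5 | 0.05 | 0.95 | 0.783 |

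The top of the assumed range is 0.025/0.283, about 9% of one standard error.

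Two features of the planned analysis make the true shift smaller:
- The change at baseline is zero by definition, so the first half-interval of the DAVG is unaffected. The multiplier on d is 1 − 0.5 × (first interval)/8. With a Day 3 sample this is 1 − 0.5 × 2/8 = 0.875. Without it (Visit 3 is optional outside the PK subgroup) it is 1 − 0.5 × 4/8 = 0.75. The 0.025 becomes 0.022 or 0.019.
- Adjusting for baseline multiplies the shift again by the slope of follow-up on baseline viral load, so it shrinks further if that slope is below 1.

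**4. Effect on LRTC**

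No direction is established. As an illustration, if two event-free presatovir subjects were excluded because a post-dose swab fell below the LLOQ, 10/100 would become 10/98 = 10.2%.

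**5. Cost of requiring a pre-dose sample**

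| n per arm | DAVG power | LRTC power |
|---|---|---|
| 100 | 0.831 | 0.937 |
| 99 | 0.827 | 0.935 |
| 98 | 0.822 | 0.932 |
| 95 | 0.808 | 0.925 |

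Enrolment stopped at 189 (SAP 1.3). At 94.5 per arm, with everyone in the FAS, power is already 0.805 and 0.923; at 90 per arm it is 0.782 and 0.910.

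**The case against.** The strongest reply is that the SAP has not changed the FAS. Its Appendix 1, footnote f, says nasal samples are collected before dosing on dosing days, and its schedule has a single Day 1 nasal sampling. The SAP also states that it is based on protocol amendment 7. On that reading the missing word is shorthand. Moreover, no SAP section says that FAS entry is tested on the value selected under 3.8.4. This stands. A reader might infer that the SAP deliberately lets treated values decide who is analysed, but the text shows only an ambiguity. Nor can any change be called undeclared, because SAP 6.5, on changes from the protocol's efficacy analyses, is redacted.

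Second, the trigger is rare by design. Protocol 6.1.2.2 has subjects randomized and dosed only after all baseline assessments are complete, so the fallback needs a site to break that order. The documents contain no data on viral load in the first hours after dosing, and a late clinic swab might follow the dose closely. This also stands: the upper inputs in the working are speculative.

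Third, SAP 3.1 fixes the analysis sets before unblinding and reports exclusions with reasons by arm. That makes an imbalance visible and prevents selection on known treatment. It does not prevent selection on a value that treatment has affected.

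Fourth, keeping late-swabbed subjects has merit, since LRTC and death or ventilation need no viral baseline. That supports a sensitivity analysis that includes them, not a post-dose baseline in the primary DAVG analysis.

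**Conclusion.** The point holds in a limited form and is minor. SAP 3.8.4 states a rule under which a post-dose value can be the baseline for the DAVG and its ANCOVA, contrary to the protocol's sampling requirement. The wording of SAP 3.1.2, read with that rule, leaves it unclear whether a subject swabbed only after dosing belongs to the FAS.

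If the drug lowers viral load before the swab, the DAVG bias is toward no difference. A reader might suspect that the rule could manufacture a viral-load benefit; through the baseline shift it works the other way. Under the assumed inputs the shift is at most about 0.025 log10, and less after ANCOVA adjustment if the follow-up slope is below 1. The number of affected subjects is unknown and probably small. The planned power figures are not in dispute.

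**What to change.** - In SAP 3.1.2, restore the pre-dose condition so that the FAS matches Protocol 8.2.1.1.
- In SAP 3.8.4, delete the post-dose fallback for the primary analysis of efficacy endpoints.
- In SAP 3.8.2 and at the start of the 3.8.4 baseline rule, replace the date-based wording with a value obtained before the time of first dose, for efficacy baselines. Deleting the fallback alone is not enough: a lone post-dose Day 1 record would still satisfy the date rule. State how a Day 1 sample with no recorded time is handled.
- List by arm the subjects without a pre-dose Day 1 sample.
- If wanted, keep the fallback as a sensitivity analysis that includes those subjects, also for LRTC and for ventilation or death.

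The cost is a few lines of SAP text and the loss of the few late-swabbed subjects from the primary FAS. From the planned 100 per arm, losing 5 per arm leaves DAVG power at about 0.81 and LRTC power at about 0.925. From the 189 actually enrolled, the same loss would put DAVG power slightly below 0.80.

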7.2.1.1. Troponin

Troponin will be collected at the visits pre-specified in the protocol: Day 1, Day 17 and Day 28 (End of study). A shift table of troponin results at postbaseline visit including those obtained for the purposes of standard of care compared with baseline values will be presented by treatment group using the following categories: normal, abnormal, or missing. The number and percentage of subjects in each cross-classification group of the shift table will be presented. Subjects with a missing value at baseline or postbaseline will not be included in the denominator for percentage calculation. No formal statistical testing is planned.

If multiple troponin results exist for one visit due to multiple troponin assay tests performed, the results obtained from Troponin I test will be used for the analysis.

All troponin results, including those not required by the protocol (see protocol Section 6.11.9.2), will be presented in the subject listings.

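### SAP 3.8.2 and 3.8.4 give opposite baseline rules for tied categorical records, and 3.8.4 omits the pre-dose time limit, so some ECG and troponin shifts have no single answer

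*SAP*

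**What the plan says.** SAP 3.8.2 defines baseline for continuous and categorical data alike. Where several measurements fall on the same day, it takes the last one before the time of first dose. Where they share a time, or no time is recorded, it averages continuous values; for categorical values, "the worst among these measurements (for categorical data) will be considered the baseline value".

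SAP 3.8.4 then sets out which record to use when there are several. Its numeric rule repeats the limit to values before the time of first dose. Its categorical rule differs in two ways:

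- On timing: "For baseline, the last available record on or prior to the date of the first dose of study drug will be selected". No clock time is mentioned.
- On records with the same time or no time: "the value with the lowest severity will be selected unless otherwise specified".

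For categorical post-baseline records, 3.8.4 first takes the one nearest the nominal day. For records with the same or no time, "the most conservative value (ie, the worst severity) within the window will be selected".

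The outputs that use these categories are the ECG shift table and the count of subjects with new ECG abnormalities (SAP 7.5), and the troponin shift table (SAP 7.2.1.1). The troponin table covers post-baseline results "including those obtained for the purposes of standard of care compared with baseline values".

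**The concern.** ECG and troponin are summarised as normal or abnormal relative to baseline. For a given post-baseline result, the baseline category alone decides whether the subject is shown as having developed an abnormality or as having had one already. If two general rules give opposite baselines, the programmer has to choose, and the plan does not say how. That choice should not be left until treatment codes are known.

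The timing gap raises a related question. Protocol 6.11.8 requires the Day 1 ECG before dosing and also requires any additional ECG done for patient care to be collected. A second ECG on Day 1 after the dose is therefore foreseeable. If it were taken as baseline, a change occurring soon after the first dose would become part of the reference value and could not be counted as new.

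**Working it through.** The plan states no figure here, so there is none to reproduce. The check sets the rules side by side and enumerates the cases.

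**Step 1: tied baseline records.** Code normal as 0 and abnormal as 1. Let b1 and b2 be two baseline records with the same time or no time, and p the post-baseline result.

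- SAP 3.8.2: baseline = max(b1, b2)
- SAP 3.8.4: baseline = min(b1, b2)
- New abnormality: p > baseline

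| Tied baseline pair | Post-baseline | Shift under 3.8.2 | Shift under 3.8.4 | New under 3.8.2 | New under 3.8.4 |
|---|---|---|---|---|---|
| 0, 0 | 0 | 0 to 0 | 0 to 0 | no | no |
| 0, 0 | 1 | 0 to 1 | 0 to 1 | yes | yes |
| 0, 1 | 0 | 1 to 0 | 0 to 0 | no | no |
| 0, 1 | 1 | 1 to 1 | 0 to 1 | **no** | **yes** |
| 1, 1 | 0 | 1 to 0 | 1 to 0 | no | no |
| 1, 1 | 1 | 1 to 1 | 1 to 1 | no | no |

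The shift-table cell differs in 2 of the 6 combinations, namely both rows with a discordant pair. The new-abnormality flag differs in 1 of the 6: discordant baseline followed by an abnormal result. In that row the worst-value rule of 3.8.2 removes the event and the lowest-severity rule of 3.8.4 keeps it. These are counts of logical cases, not estimates of how often they occur.

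**Step 2: does the text settle the conflict?** The closing words of "the value with the lowest severity will be selected unless otherwise specified" might seem to defer to 3.8.2. But 3.8.2 covers exactly the same tied or untimed records, so if 3.8.4 always gave way to it, the 3.8.4 rule would never apply. Sections 7.2.1.1 and 7.5 contain no baseline tie rule.

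**Step 3: the pre-dose limit.**

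| Place in SAP | Limit on baseline records |
|---|---|
| 3.8.2 | same-day records: before the time of first dose |
| 3.8.4, numeric | same-day records: before the time of first dose |
| 3.8.4, categorical | date of first dose only |
| 7.2.1 (parent of the troponin section) | date/time of first dose |
| 7.5 (ECG) | none stated |

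The gap therefore matters for ECG, where 7.5 gives no baseline definition of its own. For troponin, 7.2.1 already sets the time limit.

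**The case against.** The best defence is that SAP 3.8.2 is the definition of baseline, covers categorical data by name and already excludes same-day records after the first dose; 3.8.4 omits that limit but does not revoke it. SAP 3.8.3 points the same way, since it lets an unscheduled visit contribute to baseline only if it precedes the first dose, and the protocol asks for a pre-dose ECG and troponin. This stands to the extent that a post-dose ECG baseline is one literal reading of 3.8.4, not a certain outcome. It does not resolve the tie conflict. It can also be said that 7.2.1 sends multiple laboratory values to 3.8.4. That leans towards 3.8.4 for troponin, but 7.2.1 is headed as covering numeric results, and 7.5 has no such pointer for ECG.

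The defence is also right that the consequences are limited. No formal testing is planned for these tables. All troponin results and the ECG assessments are listed. Table 15.11.6.6.2, judging by its title, counts abnormal post-baseline troponin without reference to baseline.

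A reader might infer more than the documents support:

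- *That the lowest-severity rule hides events.* It makes baseline normal, so a later abnormal result counts as new.
- *That the troponin rule is a further contradiction.* When several assays exist for a visit, "the results obtained from Troponin I test will be used for the analysis", so a normal troponin I beside an abnormal troponin T is classed as normal. But this is a specific, pre-specified choice of analyte that displaces a general default. Nor does 3.8.4 always require the worst post-baseline category: first "the record closest to the nominal day for that visit will be selected", and worst severity applies only to ties.
- *That these tables rest on an FDA mandate.* The SAP revision table ties that reason to the cardiac adverse events of interest in 7.1.7. It gives detail and clarification as the reason for the troponin and ECG revisions.

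**Conclusion.** The tie rules in SAP 3.8.2 and 3.8.4 contradict each other as written, and nothing in the plan resolves the conflict. The missing time limit in 3.8.4's categorical rule is a smaller drafting gap that matters for ECG.

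For the tie conflict to change the count of new abnormalities, a subject needs baseline records that are tied or untimed, that disagree, and that are followed by an abnormal result. For the timing gap to matter, a subject needs a post-dose ECG on Day 1 and a literal reading of 3.8.4. The documents give no frequency for either, so no number of reclassified subjects can be stated. For ECG and troponin the effect is confined to descriptive shift and new-abnormality tables; other categorical variables with tied baseline records are open to the same ambiguity. No efficacy endpoint is shown to be affected. The point is worth correcting because the rule cannot be programmed as written and the choice bears on safety summaries, but its expected impact is limited.

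**What to change.** Before unblinding, put one categorical baseline rule in both 3.8.2 and 3.8.4: the last record before the time of first dose, with records sharing a time or having no time resolved to the lowest severity. Lowest severity is the better choice of the two because it lets a later abnormality count as new. It also matches the direction of 3.8.4's post-baseline tie rule, which takes the worst value. A cross-reference to the rule in 7.5 would remove any doubt for ECG.

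The cost is SAP wording only, with no change to data collection. The downside is that slightly more post-baseline abnormalities will be counted, in both arms, including some in subjects who also had an abnormal baseline record. If the SAP is already final, its Section 1 provides for recording the change in the clinical study report.
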